## Abstract

**Background:** High-flow nasal cannula (HFNC) is a device that can reduce the work of breathing (WOB) and improve oxygenation by providing a flow that matches or exceeds patient's peak inspiratory flow during tidal breathing. Despite its widespread use, there remains a lack of consensus regarding the optimal flow settings. Two new HFNC devices that can provide information regarding patient's peak tidal inspiratory flow breath by breath are recently available, which might help guide set and titrate the flow settings. This study aims to investigate the effects of different flow settings on lung impedance in a cohort of healthy volunteers by using the two new HFNC devices.

**Methods:** This prospective, randomized crossover trial will enroll adult healthy volunteers. Initially, the subject's peak inspiratory flow will be measured using a mask connected with a respiratory monitor. Subsequently, the volunteers will undergo HFNC treatment at different flow settings while their peak inspiratory flow will be continuously monitored. The primary outcome of this study is the lung aeration with different flow settings. Secondary outcomes include the lung aeration with different devices, subject's comfort at different flow settings, and the correlation between the subject's peak inspiratory flow measured by HFNC and by a mask connected with a respiratory monitor.

**Results:** N/A

**Conclusion:** N/A

## Introduction

High-flow nasal cannula (HFNC) is a widely used medical device. It can deliver flows up to 60-100 liter per minute (LPM) and maintain a consistent fraction of inspired oxygen once the set flow exceeds the patient's tidal inspiratory flow (PTIF). HFNC has demonstrated effectiveness in reducing the risk of intubation in patients with hypoxic respiratory failure, and can improve ventilation in patients with chronic obstructive pulmonary disease. These effects can be attributed to the many benefits offered by the device, including improving ventilation/prefusion matching, reducing the work of breathing, and washing out the dead space of the upper airway. Furthermore, when the flow exceeds the PTIF, a positive end-expiratory pressure (PEEP) effect is observed. This PEEP effect can be estimated by measuring the end-expiratory lung impedance (EELI), which is reported to be correlated with HFNC flows. Despite recommendations that the set flow should match or exceed the PTIF, continuous measurement of PTIF, especially during HFNC treatment, remains challenging, and there is no consensus on optimal flow settings. Therefore, a continuous PTIF monitoring could serve as an objective reference for practitioners when determining the initial flow and flow titration for different patients and under different conditions.

Two new HFNC devices, the *OmniOx HFT7500* (MEK, Paju-si, South Korea) and the *Airvo3* (Fisher & Paykel Healthcare Ltd, Auckland, New Zealand), could potentially provide the solution. The *HFT7500* can continuously measure PTIF during therapy, while *Airvo 3* provides a continuous waveform reading of the targeted flow to assess if it meets patient's demand. However, the accuracy and effectiveness of these devices remain unknown. Thus, in our study, we will measure the participants' PTIF via a mask prior to applying the HFNC and compare the flows with those displayed by the HFNC devices during treatment, particularly at different flow settings. We will also measure the lung aeration of different flows using the two devices. Our aim is to investigate the effects of different flows on the homogeneity of lung aeration. Our hypothesis is that as flow setting increases, lung aeration (EELI) will also increase.

## Methods

**Study Design:** Randomized crossover trial

**Inclusion criteria:** Healthy volunteers between 21-65 years old

**Setting:** Rush University

**Exclusion criteria:**

- 1- Chronic pulmonary diseases, including COPD, interstitial lung disease, cystic fibrosis, etc.
- 2- Uncontrolled asthma;
- 3- Pregnancy
- 4- Subjects who have cold/flu symptoms (sore throat, runny nose, fever, chills, coughing)
- 5- Nose abnormalities that can affect the functionality of the nasal prongs

**Sample size:** 26 subjects

This study is a single group comparison study designed to compare the change of EELI with different flow settings during HFNC treatment. In the study by Plotnikow et al that compared HFNC flows of 30 vs 50 L/min, they reported that mean changes of EELI from baseline were 1.12 (0.8, 2.01) at 30 L/min and 1.44 (1.05, 2.16) at 50 L/min. We use this result to calculate the sample size, with confidence level (1 -  $\alpha$ ) of 95% and power (1 -  $\beta$ ) of 80%, the sample size is calculated to be 26.

**Study Procedure:**

- 1- Study will be advertised at Rush University through a poster in a public place
- 2- Interested participants can contact the study investigator ([name]) through email or phone call which will be provided in the advertisement

- 3- Interested participants will be assessed for eligibility. If eligible, the study investigator will explain the whole study procedure and the benefits/harms to them in a private room, questions will be answered. Next, participants will be given a minimum of 30 mins to consider participating in the study. Consent will be obtained.
- 4- At the beginning, an electronic impedance tomography belt will be placed around the torso of the subjects according to their chest size. The participants will rest in a bed with head elevated at 30 degree.
- 5- Baseline measurement over 5 minutes of respiratory rate, tidal volume and PTIF will be obtained using a respiratory monitor (NICO2, Respiration, Murrysville, PA, USA) through a mask. Then the subject will be coached to breathe normally with room air for 20 mins, at the end, they will be questioned about their comfort level using a visual numerical scale ranging between 0 (extreme discomfort) and 10 (very comfortable).
- 6- HFNC devices ([HFT700](#)[HFT750](#) and Airvo 3) will be applied, three different flows will be utilized at a random sequence: 20, 40, and 60 L/min. Each flow will be utilized for 20 mins. There is a 5 min break between flows. HFNC will be removed during the break.
- 7- Between flow settings, PTIF will be measured via the mask and respiratory monitor
- 8- PTIF (measured by the [HFT700](#)[HFT750](#)) or targeted flow waveform (using Airvo 3), EELI, and respiratory rate will be monitored continuously through the procedure, and comfort level will be assessed at the end of each flow setting
- 9- The whole procedure is expected to last 3-4 hours

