## **Data Collection:**

All the following data will be collected from the participant and/or during the study.

**Demographic variables:** Age, sex, and ethnicity

**Anthropometric variables:** Height, weight

**Study variables:** Baseline PTIF, respiratory rate and tidal volume via NICO2 (Respironics, Murrysville, PA, USA). Continuous monitoring of PTIF, and respiratory rate during 3 different flow settings via two HFNC devices. Comfort level reported by participants using a visual numerical scale ranging between 0 (extreme discomfort) and 10 (very comfortable) at the end of each flow setting. Quantifying aeration homogeneity using electronic impedance tomography device by assessing EELI, regions of interest (ROI1, ROI2, ROI3, ROI4), and center of ventilation (CoV) during the 3 different flow settings.

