## **Outcomes**

- Lung aeration, EELI, respiratory rate, and comfortable level compared at baseline (without HFNC device) with 3 different flow settings
- Lung aeration, EELI, respiratory rate, and comfortable level between two HFNC devices (Airvo 3 vs HFT7500)
- PTIFs measured by the mask with respiratory monitor and by the HFT7500 device during the HFNC treatment at three flow settings.
- PTIFs measured by the mask with respiratory monitor and PTIF waveform monitored by the Airvo 3 device during the HFNC treatment at three flow settings.

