## **Data Analysis**

Kolmogorov-Smirnov will be used to test the normality of distribution for continuous variables. Based on the distribution of the variables, continuous variables (respiratory rate, PTIF and comfort level) will be reported as mean and standard deviation (SD) or median and Inter-Quartile Range (IQR). Friedman or Repeated Measures ANOVA analysis will be used to compare the differences of continuous variables between baseline and 3 flow settings with each HFNC device. Mann-Whitney or independent t test will be used to compare the differences of continuous variables between two devices. Spearman's Rho or Pearson Correlation statistical test will be used to assess the correlation between PTIF measured via mask (NICO2) with PTIF measured by the HFT7~~500~~ device. A *p*-value of < 0.05 will be considered statistically significant. Data analysis will be conducted with SPSS software (SPSS 26.0; Chicago, IL).

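### The order of the two devices is not specified; if most participants get the same device first, the Airvo 3 vs HFT7500 comparison is confounded with time

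*Combined protocol and SAP*

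**What the plan says.** The Abstract gives the design: "This prospective, randomized crossover trial will enroll adult healthy volunteers". Neither it nor the Study Design line in Methods says which factor is randomised.

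The Study Procedure, step 6, gives the only description of randomisation. Both devices are applied, and "three different flows will be utilized at a random sequence: 20, 40, and 60 L/min". Each flow lasts 20 minutes, with a 5-minute break between flows during which HFNC is removed. Step 9 expects 3-4 hours in all. The Sample size paragraph calls the study a single-group comparison and gives no device arms or allocation ratio.

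Data Collection has monitoring "during 3 different flow settings via two HFNC devices". The device comparison is a stated objective. The Abstract lists lung aeration by device among the secondary outcomes, and the Outcomes section lists "Lung aeration, EELI, respiratory rate, and comfortable level between two HFNC devices (Airvo 3 vs HFT7500" among its comparisons.

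For the analysis, the Data Analysis section says that a Mann-Whitney or independent t test "will be used to compare the differences of continuous variables between two devices". It mentions no period, sequence or carry-over term.

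**The concern.** The plan names what is randomised and leaves device order out. A site that follows step 6 literally can run one device in periods 1-3 and the other in periods 4-6 for every participant, and still meet the randomised-crossover label because the flows are shuffled.

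Under that schedule, device and half of the session are the same variable. Settling of posture, drift of the impedance signal, fatigue with the cannula or habituation in the comfort score would all appear as a device difference. Only one baseline is described, before any HFNC, so the second device's change from baseline also spans about 75 more minutes than the first device's. The planned tests have no term that could absorb this. What is at stake is the secondary device comparison for aeration, EELI, respiratory rate and comfort.

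**Working it through.** **1. Does each participant use both devices in one session?** The inputs are the durations in the Study Procedure: baseline 5 + 20 = 25 min, each flow 20 min, each break 5 min, and at least 30 min to consider participation. The break at the device switch is not given separately; 5 min is assumed.

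| Schedule | Measurement time | With 30 min consideration |
|---|---|---|
| Two devices | 25 + 6 x 20 + 5 x 5 = 170 min (2.8 h) | 200 min (3.3 h) |
| One device | 25 + 3 x 20 + 2 x 5 = 95 min (1.6 h) | 125 min (2.1 h) |

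Before set-up time, only the two-device schedule is compatible with 3-4 hours. Device order is therefore a real design factor.

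**2. How far apart are the device blocks under one fixed order?** Periods start at 0, 25, 50, 75, 100 and 125 min, so their midpoints are 10, 35, 60, 85, 110 and 135 min. The block means are (10 + 35 + 60)/3 = 35 and (85 + 110 + 135)/3 = 110. The separation is 110 - 35 = 75 min. A longer break at the switch would increase it.

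**3. Bias.** With a linear drift of b per hour, the device contrast is biased by b x 75/60 = 1.25b if everyone has the same order. With 13 participants starting on each device, half carry +1.25b and half -1.25b, so the expected bias is 0.

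**4. Illustration only.** The documents give neither a drift nor an SD for the device difference. The SD has to be borrowed from the sample-size paragraph, which concerns a flow contrast: difference 1.44 - 1.12 = 0.32, 80% power, n = 26. For a two-sided 5% paired t test (noncentral t, 25 df) this implies an SD of the paired difference of 0.56. The plan's 26 does not fix this value, because no SD or correlation is stated and other readings of the intervals also reach 26.

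False-rejection rates at a single flow under a fixed device order, for assumed drifts over 75 min:

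| Drift as share of 0.32 | Bias | Paired t, SD 0.56 | Paired t, SD 0.90 | Planned independent t, per-condition SD 0.86 | Planned independent t, per-condition SD 0.60 |
|---|---|---|---|---|---|
| 25% | 0.08 | 11% | 7% | 0.1% | about 1.5% |
| 50% | 0.16 | 29% | 14% | 0.6% | 7% |
| 100% | 0.32 | 80% | 41% | 11% | 46% |

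The independent-test columns keep the difference SD at 0.56. The value 0.86 reads the published intervals as interquartile ranges (correlation about 0.79); 0.60 is a lower alternative. The plan specifies the unpaired tests. They reject less often because they ignore the pairing, but the bias in the estimate is the same in every column.

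**5. Can analysis remove the drift?** In a simulation with n = 26, fixed device order, flows randomised within device, linear drift of 0.32 per 75 min and error SD 0.56/√2, the unadjusted device contrast was biased by 0.32. Adding a linear time term brought the mean bias to 0.00, and the standard error rose from about 0.063 to 0.136. Linear drift is thus recoverable at roughly twice the standard error.

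**The case against.** The strongest reply is that the protocol is silent on device order, not committed to a fixed one. A random sequence in a trial called a randomised crossover could be meant to cover device order, or all six device-flow periods. That stands. A reader might infer that device order is not randomised and that the comparison is confounded; the text supports only the conditional statement.

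A reader might also infer that the damage could never be undone. That is too strong. Flow varies within each device block, so a linear slope can be estimated. Step 8 monitors EELI and respiratory rate continuously, and the breaks off HFNC may give further reference readings, with some risk of carry-over. These remedies do not cover a non-linear drift or a step at the device switch. They do not help comfort either, which during HFNC is asked only at the end of each setting.

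Third, the high false-rejection rates (11%, 29%, 80%) should not be read as properties of this trial. They belong to a paired test that the plan does not use, with assumed drift and a borrowed SD.

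What does not stand is that the crossover label settles the matter. Randomising flow already satisfies it, so it gives a site no instruction about which device to start with.

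**Conclusion.** The point holds conditionally. Device order is unspecified, each participant very probably uses both devices in one session, and nothing in the design or analysis protects the device comparison if the order is the same for all or most participants. In that case the estimated device difference carries the full 75-minute drift (1.25 times an hourly linear drift), and non-linear drift, a switch effect or comfort habituation could not be fully separated from the device.

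The 75 minutes assumes six consecutive periods with 5-minute breaks. The size of the drift is unknown, and the documents do not show that any occurs. Only a secondary outcome is at risk. The primary flow comparison is not confounded in this way provided flows are randomised within each device, which step 6 should also make explicit. The change should be made before enrolment, since device order cannot be balanced afterwards.

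**What to change.** In the Study Procedure, step 6, state that device order is randomised 1:1, with 13 of the 26 participants starting on the HFT7500 and 13 on the Airvo 3, and that flow order is randomised separately within each device.

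In Data Analysis, replace the Mann-Whitney or independent t test for the device comparison with a within-subject model that has device, flow, period (1-6) and device-order terms. The unpaired tests do not suit a comparison in which each participant uses both devices.

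The cost is one protocol sentence, a randomisation list and slightly more analysis, plus the small inconvenience of setting up the devices in a different order for different participants. No participants, visits or session time are added. If random device order was already intended, the sentence simply records it.

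### The HFT7500 reads peak flow on HFNC but every mask reading is taken off HFNC, so comparing them cannot show device accuracy during treatment

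*Combined protocol and SAP*

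**What the plan says.** **Mask readings.** Study Procedure, step 5, opens with the mask: "Baseline measurement over 5 minutes of respiratory rate, tidal volume and PTIF will be obtained using a respiratory monitor". Twenty minutes of room-air breathing follow before any HFNC. Step 6 then runs each of the three flows for 20 minutes. It adds "There is a 5 min break between flows" and "HFNC will be removed during the break". Step 7 places the remaining mask readings in those gaps: "Between flow settings, PTIF will be measured via the mask and respiratory monitor". Data Collection lists mask PTIF at baseline only; the break readings appear nowhere but step 7.

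**Device readings.** Step 8 and Data Collection take these with HFNC running: "Continuous monitoring of PTIF, and respiratory rate during 3 different flow settings via two HFNC devices". For the Airvo 3, step 8 specifies a targeted-flow waveform instead of a PTIF value.

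**Purpose.** The Introduction says of the two devices: "However, the accuracy and effectiveness of these devices remain unknown". It then says the study will measure "PTIF via a mask prior to applying the HFNC and compare the flows with those displayed by the HFNC devices during treatment".

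**Outcome and analysis.** Outcomes lists "PTIFs measured by the mask with respiratory monitor and by the HFT7500 device during the HFNC treatment at three flow settings", with a parallel item for the Airvo 3 waveform. Data Analysis plans a Pearson or Spearman correlation between mask and HFT7500 PTIF, and nothing for the Airvo 3 item. The Abstract places the correlation among the secondary outcomes.

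**The concern.** The mask and the device never observe the same breathing. One reads a person breathing without support, the other the same person minutes away in time and on HFNC. The protocol gives reasons why breathing might differ between these states: the Introduction credits HFNC with lowering breathing effort and clearing upper-airway dead space, and Outcomes makes the change in respiratory rate from the HFNC-free baseline something to be tested. Nowhere does the plan state that PTIF is assumed equal on and off HFNC.

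A report that follows the Introduction would read the comparison as evidence on accuracy. An error-free device could then be marked down because breathing changed, or a biased one passed because a true change offset its bias. The missing pairing rule adds a second problem: the analyst could choose among baseline and break readings after seeing the data.

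**Working it through.** The plan states no figure for this comparison, so there is none to reproduce.

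**1. Timing, side by side**

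| Reading | HFNC | Source |
|---|---|---|
| Mask, baseline | Off | Study Procedure, step 5 |
| Mask, breaks | Off | Study Procedure, steps 6 and 7 |
| HFT7500, each flow | On | Study Procedure, step 8; Data Collection |
| Mask, with HFNC running | Not planned | – |

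**2. What a difference contains.** Write T for true PTIF. Then

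device(on) − mask(off) = [T(on) − T(off)] + [device(on) − T(on)] − mask error.

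The first bracket is change in breathing and the second is device error. Only their sum is observed.

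Illustration, with assumed values: T(off) has mean 30 and SD 6 L/min, and the mask has no error.

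| Case | Change in breathing, mean | Device error, mean | Mean difference | SD | 95% limits | r |
|---|---|---|---|---|---|---|
| A: error-free device | −5 | 0 | −5 | 4 | −12.8 to 2.8 | 0.83 |
| B: breathing unchanged | 0 | −5 | −5 | 4 | −12.8 to 2.8 | 0.83 |
| C: half of each | −2.5 | −2.5 | −5 | 4 | −12.8 to 2.8 | 0.83 |
| D: opposing | +5 | −5 | 0 | 4 | −7.8 to 7.8 | 0.83 |

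The SD of 4 is all breathing change in A and all device error in B; in C and D it is split equally (√8 each, and √(8 + 8) = 4). The limits are mean ± 1.96 × 4. The correlation is 36/√(36 × (36 + 16)) = 0.83 in every case. A, B and C produce the same data, and in D a real device bias disappears. Randomised flow order and more participants do not help, because the cause is the on/off contrast.

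**3. Random variation alone.** Suppose there is no systematic shift and the device is error-free. Let b be the between-person SD and w the within-person period-to-period SD, taken as equal on and off HFNC. Against one mask reading, r = b²/(b² + w²) and the 95% limits are ±1.96 × √2 × w. Against the mean of two mask readings the variance of the difference is w² + w²/2, so the limits are ±1.96 × √1.5 × w. With b = 8 L/min (assumed):

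| w, L/min (assumed) | r, one reading | Limits, one reading | Limits, mean of two |
|---|---|---|---|
| 3 | 64/73 = 0.88 | ±8.3 | ±7.2 |
| 4 | 64/80 = 0.80 | ±11.1 | ±9.6 |
| 5 | 64/89 = 0.72 | ±13.9 | ±12.0 |

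Any systematic on-HFNC shift adds to the apparent bias one for one.

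**4. Which mask readings sit next to which setting.** The first setting of the session has a break reading after it, but the reading before it is the baseline, separated by 20 minutes of room air. No mask reading is specified after the last setting. Device order is not stated, so it is unknown whether an HFT7500 setting falls in either position.

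**The case against.** - **The plan promises only a correlation.** Accuracy appears in the Introduction as background, and no agreement limits or accuracy criterion are planned. In the worst row above (r = 0.72, n = 26), t = 0.72 × √24/√(1 − 0.72²) ≈ 5.1, so an error-free device would still show a strong, significant correlation. This stands against any claim that the device would fail the planned test. It does not rescue the accuracy purpose: cases A to D share one correlation whether the device is biased or not.
- **No PTIF change is documented for these participants.** The physiological benefits in the Introduction are described in connection with patients who have hypoxic respiratory failure or COPD, whereas this trial enrols healthy volunteers. That stands. The point needs only that a change is possible and that equality is neither stated nor checked.
- **The size is hypothetical.** That stands too; every SD above is an assumption.
- **Three conflicting references.** A reader might infer that the Introduction, Study Procedure and Outcomes contradict one another. They do not. The Introduction's mask reading fits step 5, step 7 adds further ones, and in Outcomes the reference to treatment most naturally belongs to the device reading. The wording is loose and the pairing undefined.
- **Bracketing as a cure.** A reader might also infer that mask readings on either side of a setting separate breathing from device error. They capture off-HFNC variability only and say nothing about a systematic shift on HFNC.

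**Conclusion.** The point holds as a limit on what may be concluded. The planned comparison can describe how on-HFNC device readings relate to off-HFNC mask readings. It cannot support a statement that the HFT7500 is or is not accurate during treatment. This follows from the timing alone and needs no assumed figure. The numerical ranges do rest on assumptions: b = 8, w = 3 to 5 L/min, and equal period-to-period variation on and off HFNC.

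The reach is limited. The PTIF comparison is a secondary outcome; the primary comparison of lung aeration across flows, and the sample size based on EELI, are untouched. It would be wrong to infer that the trial as a whole is compromised. An independent reference while HFNC is running would need a different procedure, so what remains is to narrow the claim and make better use of the readings that step 7 already plans.

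**What to change.** 1. **Wording.** In the Introduction, Outcomes and Data Analysis, state the outcome and its conclusion as on-HFNC device reading versus off-HFNC mask reading, and make no claim of accuracy during treatment. Apply the same limit to the Airvo 3 item.
2. **Pairing.** Pre-specify it. For each HFT7500 setting, use the mean of the adjacent mask readings where both exist and the single adjacent one otherwise. Treat the baseline reading as non-adjacent for the first setting of the session. Compare with device PTIF from the last minutes of the setting, with that window defined in advance. Add the break mask readings to Data Collection.
3. **Analysis.** Keep the correlation and add the paired difference with 95% limits by flow setting. Beside it, report the within-person mask-to-mask SD (w) from baseline and breaks, and the matching yardstick: ±1.96 × √1.5 × w where two mask readings are averaged, ±1.96 × √2 × w where there is one. State that this accounts for random period-to-period variation only, not for a systematic on-HFNC shift.

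No new measurement is needed beyond what step 7 plans. The cost is a narrower claim about the device and a little more analysis.
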